Sternberg Task: Expose subjects to active or sham TMS to a region of the frontoparietal attention network during the Sternberg WM task. Subjects will have to maintain a series of letters in WM for a brief interval during blocks of safety and threat of shock.

NPU Task: Expose subjects to active or sham TMS to a region of the frontoparietal attention network during the NPU threat test. Subjects will be exposed to blocks in which they are either 1) safe from shock (neutral), 2) at risk of shock delivered only during a cue (predictable), or 3) at risk of shock presented randomly (unpredictable).

Outcome measures: In both studies the primary outcome measure will be anxiety-potentiated startle (APS), which is the increase in startle magnitude during periods of threat compared to periods of safety. We expect active, but not sham TMS to increase activity in the dlPFC, and therefore reduce APS in both studies.

Table of Contents

| | |
|---|-----------|
| 1. Introduction and Background | 9 |
| a. Background | 9 |
| b. Significance | 11 |
| c. Preliminary data | 11 |
| 2. Study Objectives | 17 |
| a. Primary objectives | 17 |
| 3. Subjects | 18 |
| a. Description of study populations | 18 |
| b. Inclusion criteria | 18 |
| c. Exclusion criteria | 18 |
| 4. Study Design and Methods | 19 |
| a. Study overview | 19 |
| b. Recruitment | 20 |
| c. Screening | 21 |
| d. Study procedures | 22 |
| e. End of participation | 27 |
| 5. Management of Data and Samples | 27 |
| a. Storage | 27 |
| b. Data sharing plan | 28 |
| 6. Additional Considerations | 28 |
| a. Research with investigational drugs or devices | 28 |
| b. Gene therapy | 28 |
| 7. Risks and Discomforts | 28 |
| a. Procedures | 28 |
| b. Procedures to Minimize Risks | 31 |
| 8. Subject Safety Monitoring | 32 |
| 9. Outcome Measures | 33 |
| a. Primary outcome measures | 33 |
| 10. Statistical Analysis | 33 |
| a. Analysis of data/ study outcomes | 33 |
| b. Power analysis | 33 |
| 11. Human Subjects Protection | 34 |
| a. Subject selection | 34 |
| Justification for exclusion of children | 34 |
| Justification for inclusion of other vulnerable subjects | 34 |
| Justification for exclusion of other vulnerable subjects | 34 |
| Justification for exclusion of non-English speaking subjects | 35 |
| Justification for exclusion of subjects over 50 years of aged | 35 |
| Justification for exclusion of non-right-handed subjects | 35 |

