One variant of the threat of shock paradigm is the so-called NPU paradigm, where subjects are exposed to simple cues during blocks of no threat (N), predictable threat (P), and unpredictable threat (U) (Schmitz and [name], 2012). During this paradigm, simple geometric shapes serve as cues (presented for 8 s). During the predictable threat blocks, these cues indicate that a shock may occur, while during the unpredictable and neutral blocks, these cues are not predictive of the shock. During the no threat blocks subjects are instructed that they are completely safe from shocks, and during the unpredictable blocks, subjects are instructed that they could receive a shock at any point. This paradigm provides measures of fear (e.g., fear-potentiated startle) associated with the threat cue in the P condition and of anxiety (e.g., anxiety-potentiated startle) in the N, P, and U contexts (no-cue periods). This paradigm is ideal to test the top-down inhibition hypothesis because it allows for the testing of both fear and anxiety, without adding additional cognitive demands. In addition, cue presentations during the NPU task activate the dlPFC (See below), which may reflect an implicit form of top-down emotion regulation.

The purpose of this protocol is to use TMS to determine the role of the FPN in anxiety reduction. According to our model, we have 2 hypotheses. First, suppressing activity in

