Anxiety is reduced by WM load in the Sternberg WM paradigm: Therefore, in an effort to better understand the psychological mechanisms underlying the load related anxiety reduction, we followed up the N-back studies with the Sternberg WM paradigm (Sternberg, 1966). In the Sternberg WM paradigm, subjects are presented with a series of letters, and required to maintain this series of letters in WM for a brief maintenance interval. After the maintenance interval, subjects are presented with a response prompt, which consists of a letter and a number. The letter is chosen from the study series, and the number corresponds to a position in the series. At the prompt, subjects are instructed to identify whether the position of the letter in the series matches the number. By varying the number of to-be-encoded letters in a series, it is possible to increase WM load. Because simple rehearsal is sufficient to maintain these letters (Altamura et al., 2007), this task does not require the engagement of central executive resources (Baddeley, 1992).

In these follow-up studies, we required subjects to perform the Sternberg task during periods of safety and threat. We increased WM load by manipulating the number of letters in this series, and probed subjects anxiety with the startle reflex during the safe or threat blocks. Consistent with the previous n-back studies, we found that increasing WM load reduces anxiety (APS), when anxiety is probed during the maintenance period, but not the ITI (Figure 7). This is true even though the Sternberg task typically does not engage central executive processes, suggesting that this acute anxiety down-regulation can be caused by WM components other than the central executive. However, unlike the previous n-back studies, performance was not impaired under threat of shock (Figure 6), suggesting that the central executive processes, rather than maintenance processes were impacted by anxiety in the n-back task.

[figure not shown]

Figure 6: Sternberg WM performance is not affected by threat.

Figure 7: APS is reduced during the maintenance period of high load Sternberg WM trials.

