There will be 4, 14 min runs of the experiment (2 active and 2 sham). Within each run, there will be 8 blocks (2 predictable, 2 unpredictable, 4 neutral). There are twice the number of neutral blocks to ensure that safe blocks alternate with threat (predictable or unpredictable) blocks. During half of the blocks (1 predictable, 1 unpredictable, 2 neutral), subjects will receive a continuous train of 1 Hz stimulation to the left IPS. Within each block, there will be 2 types of trials based on the delivery of startle probes. Startle probes will be presented either during the cue period, or the ITI. During the predictable and unpredictable blocks, there will be 4 trials per condition. Given that there will be twice as many neutral blocks, during these blocks there will only be 1 trial per condition. The result will be a total of 192 trials across the entire experiment (2 [active vs. sham] x 2 [neutral vs. predictable vs. unpredictable] x 2 [maintenance vs. ITI] x 2 [TMS vs. no TMS] x 2 [run repetitions] x 4 [block*trial repetitions]). Trials will last approximately 17 seconds. There will be a total of 3 shocks per run presented during either the ITI (unpredictable) or cue (predictable) periods.

Sub-study 3, NPU task: There will be 1 pre-TMS and 1 post-TMS NPU run during each TMS visit. Within each run, there will be 8 blocks (2 predictable, 2 unpredictable, 4 neutral). There are twice the number of neutral blocks to ensure that safe blocks alternate

with threat (predictable or unpredictable) blocks. Startle probes will be presented either during the cue period, or the ITI. During the predictable and unpredictable blocks, there will be 2 trials per condition. Given that there will be twice as many neutral blocks, during these blocks there will only be 1 trial per condition. The result will be a total of 192 trials across the entire experiment (2 [active vs. sham] x 3 [neutral vs. predictable vs. unpredictable] x 2 [maintenance vs. ITI] x 2 [pre-TMS vs. post-TMS] x 8 [block*trial repetitions]). There will be a total of 3 shocks per run presented during either the ITI (unpredictable) or cue (predictable) periods.

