Subjects will be informed that they can withdraw from the study whenever they wish. Sample shocks will be administered prior to the study. At this point, subjects will be explicitly asked if they wish to continue. Subjects receiving the frontal TMS will also be given a chance to experience the sensation of the TMS via electric scalp stimulation. Subjects will be given the opportunity to discontinue after this sensation screen. The experiment will also be stopped for any subject who exhibits signs of distress during any phase of the study. Subjects will be constantly monitored via closed circuit video by the AI for MRI sessions. An AI is present during TMS sessions. A credentialed staff member (RN, NP or MD) will assess the subject at the conclusion of the study or at any time if significant side effects develop. The subject will be withdrawn at any time if unable to follow the rules for participation in this study.

9. Outcome Measures

a. Primary outcome measures

The primary outcome measures will be APS reduction as a function of stimulation type, active or sham stimulation.

10. Statistical Analysis

a. Analysis of data/ study outcomes

Sternberg. APS scores will be created by subtracting the startle magnitude during the safe blocks from the startle magnitude during the threat blocks. These scores will be analyzed using a 2 [block: active vs. sham] x 2 [stimulation: TMS vs. no TMS] x 2 [interval: maintenance vs. ITI] repeated measures ANOVA.

NPU. APS scores for the cue and ITI will be created by subtracting the startle magnitude during the safe blocks from the startle magnitude during the unpredictable blocks. FPS scores will be calculated by subtracting the startle magnitude during the predictable ITI from the startle magnitude from the predictable cue. These scores (APS cue, APS ITI, FPS cue) will be analyzed using a 2 [block: active vs. sham] x 2 [stimulation: TMS vs. no TMS] repeated measures ANOVA.

b. Power analysis

In our Sternberg pilot experiment, we obtained the effect size ($f=0.72$) for our observed WM load-related decrease in anxiety. Assuming a somewhat smaller effect size ($f=0.5$) due to regression to the mean, if we set power at .95 and experiment-wise, two-tailed alpha at 0.05. Based on these parameters, we will need 48 subjects per experiment. Assuming a 15% unusable data rate and 3 subjects to initially adjust the experimental procedure, we will need 58 subjects per experiment.

11. Human Subjects Protection

a. Subject selection

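### Section 10.b sets an experiment-wise alpha of 0.05, but 10.a names no deciding APS test; tested as listed, error is about 10% in Sternberg and 8% to 19% in sub-study 2

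*Combined protocol and SAP*

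**What the plan says.** - Error rate (section 10.b): the sample size is set with the condition "if we set power at .95 and experiment-wise, two-tailed alpha at 0.05", giving 48 subjects per experiment.
- Primary outcome (section 9.a): "The primary outcome measures will be APS reduction as a function of stimulation type, active or sham stimulation". The Précis also makes APS the primary measure and adds: "We expect active, but not sham TMS to increase activity in the dlPFC, and therefore reduce APS in both studies".
- Sternberg analysis (section 10.a): "These scores will be analyzed using a 2 [block: active vs. sham] x 2 [stimulation: TMS vs. no TMS] x 2 [interval: maintenance vs. ITI", as a repeated measures ANOVA.
- NPU analysis (section 10.a): "These scores (APS cue, APS ITI, FPS cue) will be analyzed using a 2 [block: active vs. sham", crossed with TMS versus no TMS. APS is defined for the cue and for the ITI. Fear-potentiated startle (FPS) is a third score.
- Design of sub-studies 1 and 2 (section 4.d): each has two active and two sham runs, and only half the blocks within a run are stimulated. For sub-study 2: "During half of the blocks (1 predictable, 1 unpredictable, 2 neutral), subjects will receive a continuous train of 1 Hz stimulation".
- Design of sub-study 3 (sections 4.a and 4.d): one active and one sham visit, each with one NPU run before and one after stimulation.

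Section 10 contains no named primary term, no choice between APS cue and APS ITI, no testing order and no adjustment.

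**The concern.** An experiment-wise error rate describes everything that could be called a success within an experiment. Section 9.a fixes the measure and the comparison, but not the test. In the 10.a models, active versus sham enters as a main effect (block) and also through its interaction with TMS on/off. These terms answer different questions. In NPU the choice doubles, because two APS scores are analysed and neither is put first.

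If the terms are tested at 0.05 each and any one of them counts, or if the deciding term or score is settled after the data are seen, the stated 0.05 does not hold. The terms can also disagree, and the plan does not say which would then be the result.

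**Working it through.** **1. The two candidate terms are different tests.** Let aT and aN be mean APS in stimulated and unstimulated blocks of active runs, and sT and sN the same in sham runs.

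- Block = (aT + aN)/2 − (sT + sN)/2
- Block x stimulation = (aT − aN) − (sT − sN)

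Illustration: suppose active TMS lowers APS by 1 unit.

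- If only stimulated blocks change (aT = −1, the rest 0): block = −0.5 and block x stimulation = −1.
- If the effect carries over to the unstimulated blocks of the same runs (aT = aN = −1): block = −1 and block x stimulation = 0.

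So the choice can reverse the conclusion. In Sternberg, interval is a factor in the model, so both terms average over maintenance and ITI.

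**2. The plan's figure, 0.05.** One test fixed in advance gives 1 − 0.95 = 0.05. Simulation under the global null (n = 48, 40,000 runs, two-sided 0.05, equal variances and correlations) gives 0.050 for block alone and 0.052 for block x stimulation alone. The stated rate is therefore met if a single term on a single score is fixed.

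**3. Sternberg, either term counts.** Over the cells (aT, aN, sT, sN) the contrasts are (1, 1, −1, −1) and (1, −1, −1, 1). Their product sums to 1 − 1 + 1 − 1 = 0, so the tests are close to independent:

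1 − 0.95² = 0.0975

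Simulation gives 0.099, and 0.098 with cell SDs varying from 1 to 2. The Monte Carlo standard error is about √(0.1 × 0.9 / 40,000) = 0.0015.

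**4. Sub-study 2, APS cue and APS ITI.** The 2 x 2 in 10.a has no cue/ITI factor, so I take each score to have its own ANOVA. That is an inference, though the natural one. The documents do not give the correlation between the two scores, so a range is assumed.

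| What counts as success | r = 0 | r = 0.5 | r = 0.8 |
|---|---|---|---|
| Block on either score | 0.099 | 0.088 | 0.079 |
| Block x stimulation on either score | 0.100 | 0.092 | 0.079 |
| Either term on either score | 0.189 | 0.172 | 0.152 |

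For comparison, four independent tests give 1 − 0.95⁴ = 0.1855. A second simulation gave 0.185 at r = 0 and 0.173 at r = 0.5 for the last row.

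**5. Sub-study 3.** The only NPU model in 10.a crosses active/sham with TMS versus no TMS. In section 4.d the second factor of this experiment is pre-TMS versus post-TMS. The written model does not describe the data, so no error rate is calculated for it.

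The error rates depend hardly at all on n. Whether 48 follows from the assumed effect size is a separate question.

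**The case against.** **Experiment-wise may only mean 0.05 for each of the three experiments.** The phrase appears once, in a sample-size sentence that counts subjects per experiment. This reading is plausible, and no error across experiments is counted here. But several APS tests remain within each experiment, and one of them still has to decide.

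**Section 9.a points plainly to active versus sham, so the block main effect was meant.** This has weight. The Précis sentence that favours the interaction is a directional hypothesis about the dlPFC, whereas sub-studies 1 and 2 stimulate the left IPS. Even so, 9.a names no ANOVA term, and the unstimulated blocks in each run make the interaction a natural candidate. Settling on block would still leave cue versus ITI open in NPU, at about 8–10%.

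**The background already indicates the score.** Section 1.a links the NPU task to "anxiety (e.g., anxiety-potentiated startle) in the N, P, and U contexts (no-cue periods", which suggests ITI. However, section 1.c reports raised startle in both cue and ITI under unpredictable threat, and 10.a defines APS for both.

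**Stronger readings that do not hold.** A reader might count all four active-versus-sham terms in the Sternberg ANOVA and quote 18–19%. That requires the two interactions with interval to count as successes on their own, which no section plans. A reader might also add FPS to the NPU count, but 9.a and the Précis place APS above it. Nor do the documents plan to pick the favourable term; they only fail to exclude it.

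**Conclusion.** The concern holds in limited form. The ranking of APS over FPS is settled; the deciding term is not, nor in NPU the deciding APS score. The sizes in steps 3 and 4 are conditional: they assume unadjusted two-sided 0.05 tests, a global null, and that any listed candidate would count. The NPU range also rests on assumed correlations. They show what the text permits, not what the investigators intend. If a single test was always meant, the error is 5% and writing it down closes the point. The mismatch of model and design in sub-study 3 stands independently of any error rate.

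**What to change.** Before data are analysed, amend section 10:

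1. Name one primary active-versus-sham term on one APS score per experiment, at two-sided 0.05.
2. Sub-study 1: for example block x stimulation, stating whether it is averaged over interval or taken at one interval. The choice matters because section 1.c reports that "we found that increasing WM load reduces anxiety (APS), when anxiety is probed during the maintenance period, but not the ITI".
3. Sub-study 2: for example block x stimulation on one stated APS score, cue or ITI.
4. Sub-study 3: replace TMS versus no TMS with pre versus post, and name active/sham x pre/post on the same APS score.
5. Test the remaining active-versus-sham APS and FPS terms as secondary, with Holm adjustment within each experiment.
6. State whether experiment-wise means within each experiment or across all three.

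The cost is a few sentences and no extra subjects. The downside is that an effect in a term, interval or score that was not chosen can be claimed only as an adjusted secondary result.

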A healthy volunteer consent is submitted with this protocol. The consent form contains all required elements.

15. Data and Safety Monitoring

a. Data and safety monitoring

Data and safety will be monitored by the Principal Investigator. This study will be monitored by an independent safety monitor. [name] will serve as the independent monitor for this study.

Independent Safety Monitor

| Name, Degree | Branch/Institute | Bldg/Rm | Phone | E-mail |
|--------------------|------------------|------------------|--------------|-----------------------|
| [name] | NIMH//BEB/SBE | 10-CRC 2-5330 | [contact] | [contact] |

b. Data and safety monitoring plan

The PI will prepare a report on data and safety parameters for the Independent Monitor annually. The Independent monitor will provide a written monitoring report to be submitted to the IRB at the time of continuing review.

c. Criteria for stopping the study or suspending enrollment or procedures

In the event of unanticipated problems or serious side effects, the Principal Investigator and/ or the ISM may decide to stop or suspend the study. The Combined Neuroscience IRB safety subcommittee may also decide to stop or suspend the study for safety reasons. Safety events that would warrant suspension or stopping of the study include repeated serious adverse events related to the study procedures.

The study will be suspended if there is any UP or SAE until the MAI and IRB review the event and approve continuation.

16. Quality Assurance

a. Quality assurance monitor

Quality assurance will be monitored by the PI and research team and the NIMH Office of Regulatory Compliance (ORO).

b. Quality assurance plan

ORO monitors intramural research studies to ensure compliance with GCP, organizational policies and regulations. Audit frequency is determined by the ORO SOP based on the study level of risk. Results of ORO audits are provided to the PI, The Clinical Director and the CNS IRB. This study will undergo audits at least once every three years and for cause.

17. Reporting of Unanticipated Problems, Adverse Events and Protocol Deviations

The Principal Investigator is responsible for detecting, documenting, and reporting unanticipated problems, adverse events (AEs), including serious adverse events (SAEs), and deviations in accordance with NIH policy, IRB requirements, and federal regulations. Relatedness to the research of all serious adverse events will be determined by the PI in consultation with the CD.

Serious unanticipated problems, serious adverse events (including deaths) that are not unanticipated problems, and serious protocol deviations will be reported to the IRB and CD as soon as possible and in writing not more than 7 days after the PI first learns of the event. Not serious unanticipated problems and not serious deviations will be reported to the IRB and CD as soon as possible and in writing not more than 14 days after the PI first learns of the event. Written reports will be submitted in PTMS.

All adverse events, deviations, and unanticipated problems will be summarized and reported at the time of Continuing Review.

a. For Drugs and Biologics

Not applicable.

b. For Devices:

Not applicable.

18. Alternatives to Participation

Subjects do not receive any treatment in this study or forego any treatment in order to participate in this study. The alternative, therefore, is not to participate.

19. Privacy

All research activities will be conducted in as private a setting as possible.

20. Confidentiality

a. For research data and investigator medical records

We will actively protect confidentiality of the subjects and the data in each step. Information will be stored using a confidential case number, and no identifiers (name, address, etc.) will be used that could allow direct linking of database information to individual subjects.

Data will be kept in password-protected computers. Only study investigators will have access to the data with personal identifying information. Results will be published as group data without the use of characteristics that would identify individual subjects.

The PI will train study staff regarding obtaining and handling potentially sensitive and private information about NIH employees and staff through staff discussions and written branch/section procedures. Information about sensitive information (e.g. drug and alcohol use, specific medical diagnoses) will be in the participant's NIH medical record.

b. For stored samples

Not applicable.

c. Special precautions (e.g. certificate of confidentiality; attach documentation if certificate used)

Data will be stored using codes that we assign. Data will be kept in password-protected computers. Only study investigators will have access to the data.

21. Conflict of Interest

a. Distribution of NIH guidelines

NIH guidelines on conflict of interest have been distributed to all investigators.

b. Conflict of interest

There are no conflicts-of-interest to report.

25. Attachments/ Appendices

- Eligibility checklist

- Recruiting advertisements
- PRPL Questions

26. Consent Forms

- Healthy volunteer consent
- Pilot consent form
- Offline consent form
